4.3 Other Variables and Covariates

Additional primary endpoint (longitudinal follow up, not part of this study - application for additional funding after successful completion of the 2nd screening round):

1. All cause mortality rates and major adverse cardiovascular event (MACE: nonfatal stroke, nonfatal myocardial infarction, and cardiovascular death) rate in the reporting group vs. non-reporting group at year 5 and year 10.
2. Long-term smoking cessation rates in the emphysema reporting group vs. non-reporting group at year 5 and year 10.

5. STATISTICAL ANALYSIS PLAN

5.1 Statistical Methods – General Aspects

5.1.1 Primary and key-secondary Objective(s):

The primary and key-secondary endpoints of this study will be calculated from the following two fourfold tables summarizing the distribution of included patients and patients with detected lung cancer:

Table 1

Number of Participants by Screening Eligibility			
		NELSON	
		+	-
PLCO _{m2012}	+	A	B
	-	C	D*

Table 2

Number of detected lung cancers by Screening Eligibility			
		NELSON	
		+	-
PLCO _{m2012}	+	a	b
	-	c	d*

Please note that * indicates patients with a low risk score, which are both PLCO and LLP negative at inclusion.

PPV

PPV NELSON = $(a+c) / (A+C)$; PPV PLCO = $(a+b) / (A+B)$.

Proportion of lung cancer detected

Secondarily, proportion of lung cancers detected will be calculated as $\text{prop_lung(PLCO)} = (a+b) / (a+b+c+d^*)$ and $\text{prop_lung(NELSON)} = (a+c) / (a+b+c+d^*)$.

Additionally, also the proportion of lung cancers detected in the identified high-risk population (PLCO or NELSON positive) will be calculated, using $(a+b+c)$ as denominator and the proportion of individuals selected for screening within the low-risk population will also be calculated using $(A+B+C+D^*)$ as a denominator.

Proportion of individuals selected for screening

The proportion of individuals selected for screening (within the high-risk population) will be calculated as $\text{prop_screening(PLCO)} = (A+B) / (A+B+C)$ and $\text{prop_screening(NELSON)} = (A+C) / (A+B+C)$.

Specificity

Specificities of the risk scores will be calculated as $\text{spec(PLCO)} = (C+D^* - c-d) / (A+B+C+D^* - a - b - c - d^*)$ and $\text{spec(LLP)} = (B+D^* - b-d^*) / (A+B+C+D^* - a - b - c - d^*)$.

Sensitivity

The sensitivities correspond to the proportions of lung cancer detected in the overall population.

The primary and key-secondary endpoints will be compared between PLCO score and NELSON inclusion criteria in a hierarchical at a two-sided type-I-error of 5% to control the overall type-I-error at 5% (according to the hierarchy of endpoints outlined above). As the primary analysis, for testing the null-hypothesis of no difference between the risk scores regarding the proportion of lung cancers detected, McNemar's Test will be used.

Statistical testing

For testing the null-hypothesis of equal positive predictive values, the weighted generalized score statistic developed by Kosinski et al. (20) will be used.

For testing the null-hypothesis of no difference between the risk scores regarding the proportion of individuals selected for screening, McNemar's Test will be used.

Description of the primary analysis and population:

The primary analysis will be conducted of all volunteers within the overall study population after 2 LDCT screening rounds.

5.1.2 Secondary Objective(s): Calculation of Epidemiological Measure(s) of Interest (e.g. hazard ratios, incidence rates, test/retest reliability)

1. Rate/rate ratio of initiation of cardiovascular treatments (in particular lipid-lowering) in the calcium score reporting group vs. the non-reporting group after year 1 of study:

2. Efficiency of nodule management algorithms:

Based on the two alternative management algorithms (LungRads1.1 alone or LungRads1.1 + PanCan) patients are sorted into three management groups: (a) next surveillance scan, (b) early recall scan, or (c) diagnostic evaluation recommended. For one algorithm to be more efficient, the following criteria must both be fulfilled

- i. The number of patients without cancer sorted in the category (a) is higher AND
- ii. The number of patients with lung cancer sorted into category (b) or (c) is higher.

3. Success of screening program. Based on all individuals enrolled. Definition of success is calculated using:

a. Response rate (number of responses/overall number contacted), number of drop-outs, effectiveness of patient recruitment via mailings vs. GPs referrals (individual response rates)

b. Percentage of subjects meeting all inclusion/exclusion criteria

c. Repeatability of the PLCO score

d. Percentage of subjects receiving an adequate low-dose CT scan according to DRG guidelines (number of diagnostic CTs/number of all CTs)

4. Quality of screening program.

a. CT reading performance (2nd reader vs. CAD vs. AI)

b. Frequency of detection and management of incidental findings from low dose chest CT (emphysema, coronary heart disease, etc.)

c. Subsequent identification of biomarkers with predictive value / correlation with positive LDCT findings / cancer risk

5. Smoking cessation

a. Success of smoking cessation counseling based on number of participants quitting with or without revealing additional health risks (emphysema score, coronary calcium score or both).

6. Blood-based and exhalation- based biomarkers

a. Evaluation of various blood-based or exhalation- based biomarkers in positive LDCT cases with subsequent biopsy on the positive predictive value of the LDCT test.

7. Cost-effectiveness analysis

a. Cost-effectiveness modeling comparing screening costs and mortality benefits from lung cancer, cardiovascular and all-cause mortality (performed by Center for Health Economics Research Hannover (CHERH, DZL funding)

b. Comparison of patient recruitment strategies: Cost-effectiveness of register-based mailing campaign vs. GP referrals in terms of recruitment of qualified screening subjects (CHERH, DZL funding).

5.1.3 Exploratory Objective(s): Calculation of Epidemiological Measure(s) of Interest (e.g. hazard ratios, incidence rates, test/retest reliability)

Additional primary endpoint (longitudinal follow up, not part of this study - application for additional funding after successful completion of the 2nd screening round):

1. Mortality rates and major adverse cardiovascular event (MACE) rate in the reporting group vs. non-reporting group at year 5 and year 10 (not part of this funding period).

2. Long-term smoking cessation rates in the emphysema reporting group vs. non-reporting group at year 5 and year 10 (not part of this funding period).

5.2 Bias

5.2.1 Methods to Minimize Bias

Randomization: Subjects included in the screening study will be randomized prior to receiving the initial LDCT scan. Randomization will not affect the procedure and the schedule of the cancer screening process but only determine the allocation of the participants of the coronary calcium score and emphysema score to the reporting and the non-reporting group. Randomization ratio of 1:1 and a 2-factorial design ($\frac{1}{4}$ calcium score only; $\frac{1}{4}$ emphysema score only, $\frac{1}{4}$ both; $\frac{1}{4}$ none) will provide equally sized groups of patients in both groups including age and sex stratification.

Sampling bias: To minimize sampling bias we randomly select volunteers in the age group 55-79 from the local general population registry database (“Einwohnermeldeämter”) to be contacted via mail at each study center. Additional recruitment efforts via GP or public media may introduce a sampling bias; however, this recruitment strategy reflects the real world setting of a future German national lung cancer-screening program. Additionally, we will track and analyze the recruitment pathways in the HANSE study.

5.2.2 Adjustment for Multiple Comparisons

The primary and key-secondary endpoints will be tested in a hierarchical order, thereby controlling the overall type-I error rate at 5%. Therefore, no correction of p-values for multiple testing needs to be performed. All secondary parameters will be considered explorative.

Strengths and Limitations

Strengths

Importantly, the results and the innovative workflow infrastructure of this study should pave the way for an effective comprehensive screening program in Germany. Especially, novel results about the definition of the high-risk population, the inclusion of cardiovascular and lung comorbidity, smoking cessation and cost-effectiveness will guide the future German lung cancer screening program.

Limitations:

This study is designed as a reference case for a nationwide lung cancer screening program, which both suffer from limitations. The voluntary participation may introduce a certain bias and may not reveal all high-risk cases. In addition, clinically not apparent lung cancer cases in the low-risk population will be missed, since this group will not receive a LDCT. However, we follow-up smokers, who did not meet the risk score inclusion criteria and were willing to participate in the study, after 5 years to calculate the proportion of clinically detected lung

cancers, which were missed due to non-inclusion in the high risk group. This will generate important data for the ethical and economical discussion of risk-based inclusion for lung cancer screening.

The assessment of coronary calcium scores is usually performed on normal dose ECG-gated CT. However, recently it has been shown that coronary artery calcium scoring is feasible on non-ECG-gated LDCT. Furthermore, the used Coreline software has an innovative and fully automated algorithm especially developed for non-ECG gated Coronary calcium score on LDCT.

Due to the 36 month time horizon of the study, the endpoint ‘initiation of cv treatment’ was selected, rather than a clinically more meaningful endpoint, such as 10 year cardiovascular mortality, for example. However, the investigators will seek additional funding to continue the coronary calcium part of the study in order to evaluate cardiovascular and all-cause mortality at year 10 follow-up.

5.3 Sample Size and Power Calculations

To be assessed for eligibility: n = 350 000

To be allocated to trial: n = 5500 + all recruited volunteers with low risk scores/low NELSON criteria (low risk group)

To be analysed: n = 5000 + 7100 low risk group

(i) Power calculation for the primary endpoint

Sample size calculation is based on data from the German Health Update study (GEDA; “Gesundheit in Deutschland aktuell”) - a health monitoring program consisting of cross-sectional surveys conducted by the Robert Koch Institute to provide data on health and disease, health determinants and health behaviors from nationally representative samples of adults in Germany (20). Between 2008 and 2013, three GEDA studies were carried out, in 2008–2009, 2009–2010 and 2012–2013, involving a total of 62,606 computer assisted telephone interviews (23, 24). Based on this dataset the PLCO risk score was adjusted to a level (5-year risk of 1.314%, or 6-year risk of 1.58% [rounded]) were the NELSON inclusion criteria and the PCLO risk score are equally weighted in the German population aged 55–79 to include the same amount of volunteers in each group (table 3)

Table 3:

Risk threshold of 0.01314 (5y risk, weighted, scaled to 5000 participants) - Eversmokers aged 55-79				
Nelson				
	0		1	
PLCO	0 7095.8 (21.8)	1070.25 (9.8)		
	1 1072.73 (27.0)	2857.04 (112.2)		

Number of ever smokers (predicted cancers) GEDA dataset (23, 24).

Between parentheses are the 5-year case numbers predicted by the PLCO model.

In a study by Hüsing & Kaaks (24) this model was found to accurately predict absolute lung cancer incidence compared to incidence actually observed (cancer registry data).

However, for power calculations one cannot directly assume that predicted 5-year incidence corresponds to the number of LC cases that will be detected by two CT screenings over a 1-year interval.

To estimate the number of expected CT-detected cases (two screens, 1-year interval) we extrapolated from observations in the LUSI trial. LUSI included participants 50-69 years of age who met the smoking criteria of NELSON. In a total of 2029 participants in the screening arm, 34 LC cases were detected in the first two screening rounds (22 at prevalence screen, and 12 at the first incidence screen).

From GEDA data, using the PLCO model, we estimated that, compared to individuals who meet the inclusion criteria of LUSI (age 50-69, and smoking criteria identical as in NELSON) the (5-year) LC incidence is 1.72 times higher for individuals in the higher age range (55-79, + NELSON smoking criteria) chosen for the present study.

For the present study, we thus estimated an expected overall number of CT-detected cases of $144:34 \times 5000/2029 \times 1.72 = 144$

We assume that these 144 CT-detected cases will be proportionally distributed as those in Table 3 (i.e., as with predicted 5-year incidence without screening).

The numbers in Table 3 suggest that the PPV of the PLCO (risk-based, with 6-year risk threshold of 1.58%) will be 14% higher than the PPV of NELSON.

For comparing positive predictive values from a paired diagnostic study, the weighted generalized score statistic proposed by Kosinski (20) will be used to test the Null-hypothesis of the PPVs being equal for Nelson and PLCO.

Using a two-sided type-I error rate of 5%, the power of the primary comparison was estimated with a simulation study based on the above described proportions. Assuming an overall number of 5000 patients who are selected by the Nelson or the PLCO criterion, and number of patients which are positive by Nelson or PLCO only are simulated as a realization of a multivariate variable with n=5000 and proportions (2857/5000, 1070/5000 and 1072/5000 respectively) as

n_{both} , n_{Nelson} and n_{PLCO} . Subsequently, the number of cancers detected was calculated from independent Binomial variables for each of the following conditions.

Number of cancers in the group of patients who are Nelson and PLCO positive: $\text{Bin}(n_{\text{both}}, (144/149)*(112/2857))$

Number of cancers in the group of patients who are Nelson positive and PLCO negative: $\text{Bin}(n_{\text{Nelson}}, (144/149)*(10/1070))$

Number of cancers in the group of patients who are Nelson negative and PLCO positive: $\text{Bin}(n_{\text{PLCO}}, (144/149)*(27/1072))$

The empirical power was estimated as the proportion of 10,000 simulation runs, where the weighted generalized score statistic (20) applied to the simulated data showed a p-value smaller than 5%.

Based on the above procedure, the estimated power to reject the null-hypothesis of equal PPVs between the NELSON and the PLCO score is 80,3%.

For the HANSE study the calibrated threshold for the PLCO 5 year risk score of 1,314% was converted to a 6year threshold of 1,58% , because the original PLCO risk score calculates the 6year risk and thus the original calculators by Tammemägi et al. can be used for the HANSE study (13).For this conversion linearity between year 5 and 6 was assumed.

(ii) Sample size for the evaluation of **initiation of cardiovascular therapy** within 1 year after randomization has been calculated using Chi-Square Test and two-sided type-I-error rate of 5% based on the results of the ITALUNG study (15,16), where for 44% of all patients coronary artery calcification (CAC) was detected. In the ITALUNG study, 63% of patients with CAC were on cardiovascular treatment without receiving results of their low dose CT screening. For this study, where the patients are randomized to either reporting or non-reporting of CT screening results, we conservatively assume that the non-reporting group shows a rate of cardiovascular treatment of 68%. In contrast, as an effect of reporting the screening results, we assume that in the reporting group 73% of patients receive cardiovascular treatment, so the effect of reporting the CT results is assumed to be an increase of 5 percentage points in the cardiovascular treatment rate. Acknowledging that only 44% of all patients are assumed to show CAC on low dose CT, the expected difference between the reporting and non-reporting group is $(73\% - 68\%) * 44\% = 2.2\%$. Equivalently, the assumed rate ratio between the reporting and non-reporting group is $(73\% * 44\%) / (68\% * 44\%) = 1.07$. With 2,500 patients randomized to each arm and using a Chi-Square Test with a two-sided type-I-error rate of 5% for testing the null-hypothesis of no difference between the groups, the statistical power is 97%.

(iii) To evaluate the power of potential **longitudinal follow-up** studies based on this screening trial, the power for the 10 year mortality endpoint has been calculated based on the results of the NELSON study using a Chi-Square Test with a two-sided type-I-error rate of 5% for testing the null-hypothesis of no difference in 10-year cardiovascular mortality rates between the

reporting and non-reporting groups. In line with the results of the NELSON study, we assume a 10 year cardiovascular mortality rate in the non-reporting group of 2.7%.

[figure not shown]
Assuming a rate ratio of 0.6 between the reporting and non-reporting group (or equivalently, a 10-year mortality rate of 1.6%), the difference between the reporting and non-reporting group can be shown with a power of 75%.

Conclusion: With an overall sample size of 5,000 subjects (and 2,500 volunteers randomized to the reporting and non-reporting group) the study is well-powered to investigate the primary hypothesis, evaluate potential cardiovascular benefit and provide the basis to investigate mortality in a follow-up study.

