For the HANSE trial, 5,000 participants aged 55-79y who meet the NELSON and/or PLCO_{M2012} 6 year risk >1.58% selection criteria will be included. Participants will undergo baseline and 1-year screening under defined conditions using low-dose computed tomography in three specialized lung cancer centers in northern Germany.

Standardized and quality-assured image analysis will be conducted using state-of-the-art artificial intelligence (AI)-based detection and nodule measurement software (AVIEW, Coreline Soft Company Ltd., South Korea) to support the radiologist. CT assessment of lung nodules will be done according to LungRADS 1.1 criteria, as well as volume doubling time according to the European position statement on lung cancer screening (14). Additionally, this trial integrates different recruiting strategies, a smoking cessation counselling program, includes a cost-effectiveness modelling, cardiovascular and lung comorbidity assessment, different lung nodule management strategies (Lung RADS 1.1. vs. PanCan vs. AI) and explores blood-based biomarkers in positive LDCT cases.

An additional objective of the HANSE study is to provide evidence for the potential of low dose CT in the diagnosis of diseases other than lung cancer, such as emphysema, but also cardiovascular diseases, which to date has only been suggested by retrospective analyses of LDCT studies (15, 16). Low dose CT does allow to examine the coronary calcium score (Agatston score (17)), indicative of the coronary plaque status which has shown to correlate with the rate of future myocardial infarction, stroke and death due to cardiovascular disease (18). The trial will assess whether reporting of the score may have consequences in individuals with a positive

coronary calcium score seeking specialist consultation and initiating preventive cardio-vascular therapy.

The trial will further encompass a smoking cessation program and smoking cessation rate under the different experimental settings will be determined at 1-year follow-up. Specifically, the consequences on smoking status will be compared between the non-reporting group, the calcium score reporting group, the emphysema score reporting group vs. the non-reporting group in order to document a potential impact of reporting.

Additionally, this design feature allows to analyse long-term smoking cessation rates and mortality in a follow-up study at year 5 and 10 (not part of this funding period).

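### The 144 expected cancers apply a NELSON-eligible yield to all 5,000 NELSON-or-PLCO participants; the count consistent with Table 3 is 138, and primary power is about 78.2% (rounded cells) or 79.4% (Table 3 cells), not 80.3%

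*Protocol*

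**What the plan says.** Section 5.3 (i), repeated in the synopsis under Statistical Analysis (i), builds the primary power in three steps.

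- **Yield.** LUSI detected 34 cancers among 2,029 screened participants over two rounds. Those participants were people "who met the smoking criteria of NELSON", aged 50–69. From GEDA data, incidence is put at "1.72 times higher for individuals in the higher age range" (55–79), again for people meeting the NELSON smoking criteria.
- **Count.** The protocol then states that "we thus estimated an expected overall number of CT-detected cases of" 144, with the arithmetic 34 × 5000/2029 × 1.72. The 5,000 is defined in the simulation paragraph: "Assuming an overall number of 5000 patients who are selected by the Nelson or the PLCO criterion". Section 1.2 describes the same group as "5,000 participants aged 55-79y who meet the NELSON and/or" PLCO criteria.
- **Distribution and power.** "We assume that these 144 CT-detected cases will be proportionally distributed as those in Table 3". The three binomial rates carry the factor 144/149. The result is that "the estimated power to reject the null-hypothesis of equal PPVs between the NELSON and the PLCO score is 80,3" per cent, and the section concludes that "the study is well-powered to investigate the primary hypothesis".

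**The concern.** A yield estimated in one population is applied to a wider one. Both inputs to the yield refer to NELSON-eligible people, but the multiplier is the union of NELSON-positive and PLCO-positive people. Table 3 shows that the two groups do not share the same risk, because the PLCO-only cell has a lower predicted rate than the NELSON-positive cells combined. The protocol adjusts the LUSI yield for age but not for this difference in selection, although Table 3 supplies the figures for it.

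The steps therefore disagree. Once the 144 cases are spread as in Table 3, the yield in NELSON-positives is no longer the one that the preceding lines derived. At stake are the expected case count and the only power figure given for the primary comparison. The mismatch makes both more favourable than the protocol's own inputs allow.

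**Working it through.** **Inputs (all from Section 5.3)**

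- LUSI: 34 cases in 2,029 participants. Age-range factor: 1.72.
- Table 3, persons (predicted cases): both positive 2857.04 (112.2); NELSON only 1070.25 (9.8); PLCO only 1072.73 (27.0).
- NELSON-positive: 2857.04 + 1070.25 = 3,927 persons and 112.2 + 9.8 = 122.0 cases.
- Union: 5,000 persons and 122.0 + 27.0 = 149.0 cases.
- Simulation cells as printed: 2857/1070/1072 persons, with 112/10/27 cases.

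**Step 1. Reproduce the 144.** 34 × 5000/2029 × 1.72 = 144.1. The multiplication is right.

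**Step 2. Reproduce the 80.3%.** I reran the protocol's simulation: multinomial cell sizes with N=5,000, independent binomial cancers, and a two-sided 5% test with the weighted generalized score statistic

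T = (PPV_NELSON − PPV_PLCO)² / {[p(1−p) − 2C] (1/n_NELSON + 1/n_PLCO)},

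referred to chi-square with 1 df. Here p is the pooled PPV and C = [a(1−p)² + (A−a)p²]/(n_NELSON + n_PLCO), with A persons and a cancers in the both-positive cell. With 144 cases, the printed cells and 400,000 runs, power is 79.9%. The Monte Carlo standard error of the protocol's 10,000 runs is √(0.8 × 0.2/10,000) = 0.4 points, so the stated 80.3% reproduces.

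**Step 3. Compare the risks in Table 3.**

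- NELSON-positive: 122/3,927 = 3.11%
- PLCO only: 27.0/1,073 = 2.5%
- Union: 149/5,000 = 2.98%
- Ratio of union to NELSON-positive: 0.959

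**Step 4. Show the inconsistency.** The yield derived for NELSON-eligible people is 34/2029 × 1.72 = 2.88%. Spreading 144 as in Table 3 gives 144 × 122/149 = 117.9 cases in NELSON-positives, and 117.9/3,927 = 3.00%. The same group has two yields.

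**Step 5. Find the count that satisfies both steps.**

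- NELSON-positives: 34/2029 × 1.72 × 3,927 = 113.2
- Union, distributed as in Table 3: 113.2 × 149/122 = 138.2
- Check: 144.1 × 0.959 = 138.2

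That is about 6 cases, or 4%, fewer.

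**Step 6. Power at N=5,000 (400,000 runs).**

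| Cells | 144 cases | 138.2 cases | Loss |
|---|---|---|---|
| Rounded, 112/10/27 | 79.9% | 78.2% | 1.7 points |
| Table 3, 112.2/9.8/27.0 | 81.0% | 79.4% | 1.6 points |

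Repeat runs with other seeds vary by about 0.1 point.

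**Step 7. Scale.** The exact Poisson 95% interval on 34 cases is 23.5 to 47.5. Carried through in proportion to 138.2, it gives about 96 to 193 expected cases and power of about 62% to 90% on the rounded cells.

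**The case against.** The strongest reply is that this is an extrapolation assumption and not a miscalculation. The 144 is labelled as an estimate, it is arithmetically correct, and the 80.3% follows from it. The shift of 6 cases is far inside the uncertainty of 34 LUSI events. The corrected count still rests on the assumption that CT-detected cases follow predicted incidence cell by cell. That assumption also produces the 14% PPV advantage and matters more for power than the choice between 144 and 138.

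Most of this stands, and it limits the point to a consistency correction. It does not remove the point. The protocol nowhere says that it treats the two groups' yields as equal, and Table 3 shows that they are not. The LUSI uncertainty runs in both directions, whereas the mismatch runs in one direction only.

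A second reply concerns the headline power. Quoting only 78% against 80.3% would also charge the plan for its rounding of the cells (9.8 to 10, and so on), which costs about 1.1 points on its own (81.0% against 79.9% at 144 cases). This is right. Table 3's own figures give 79.4%, so both values have to be shown.

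A reader might infer that the simulation was run wrongly, or that the trial is underpowered and needs more participants. The documents support neither. The simulation reproduces from its inputs, and the protocol declares no power target that 78% or 79% would miss.

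**Conclusion.** The point holds as a minor inconsistency. The expected number of CT-detected cancers should be 138, not 144. Primary power at N=5,000 is about 78.2% on the rounded simulation cells or about 79.4% on Table 3's figures, against 80.3% stated. The like-for-like loss is 1.6 to 1.7 points.

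This rests on the protocol's own inputs: the LUSI yield, the 1.72 factor, Table 3, and the assumption that detected cases are distributed as in Table 3. The correction makes these agree with each other. It does not make the estimate more precise, since the 34 LUSI cases alone leave power anywhere from about 62% to 90%. The conclusion that the study is well powered becomes slightly less favourable but is not overturned.

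**What to change.** In Section 5.3 (i) and in the synopsis under Statistical Analysis (i):

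- Derive the count as 34/2029 × 1.72 × 3,927 = 113 in NELSON-positives, then × 149/122 = 138 overall.
- Replace 144 by 138 in the sentence on how cases are distributed, and 144/149 by 138/149 in the three binomial rates.
- Rerun the simulation and restate the primary power at N=5,000 as about 78% if the rounded 112/10/27 cells are kept, or about 79.4% if Table 3's 112.2/9.8/27.0 are used. Say which cells were used.

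The cost is one rerun of an existing simulation, a few corrected figures in two places, and a stated power about 1 to 2 points lower. The test, the endpoint and the enrolment number do not change.
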